14.2 Case Report Forms and Submission

Generally, clinical data will be electronically captured in the EDC system and correlative results will be captured in the EDC system or other secure database(s). If procedures on the study calendar are performed for standard of care, at minimum, that data will be captured in the source document. Select standard of care data will also be captured in the EDC system, according to study-specific objectives.

The completed dataset is the sole property of the sponsor-investigator's institution and should not be exported to third parties, except for authorized representatives of appropriate Health/Regulatory Authorities, without permission from the sponsor-investigator and HCRN.

14.3 Record Retention

To enable evaluations and/or audits from Health Authorities/HCRN, the site investigator agrees to keep records, including the identity of all subjects (sufficient information to link records; e.g., hospital records), all original signed informed consent forms, copies of all source documents, and detailed records of drug disposition. All source documents are to remain in the subject's file and retained by the site investigator in compliance with the site contract with HCRN. No records will be destroyed until HCRN confirms destruction is permitted.

14.4 Confidentiality

There is a slight risk of loss of confidentiality of subject information. All records identifying the subjects will be kept confidential and, to the extent permitted by the applicable laws and/or regulations, will not be made publicly available. Information collected will be maintained on secure, password protected electronic systems. Paper files that contain personal information will be kept in locked and secure locations only accessible to the study site personnel.

Subjects will be informed in writing that some organizations including the sponsor-investigator and his/her research associates, HCRN, BMS, IRB, or government agencies, like the FDA, may inspect their medical records to verify the information collected, and that all personal information made available for inspection will be handled in strictest confidence and in accordance with local data protection laws.

If the results of the study are published, the subject's identity will remain confidential.

15 ETHICS

15.1 Institutional Review Board (IRB) Approval

The final study protocol and the final version of the informed consent form must be approved in writing by an IRB. The site investigator must submit written approval by the IRB to HCRN before he or she can enroll subjects into the study.

The site investigator is responsible for informing the IRB of any amendment to the protocol in accordance with local requirements. In addition, the IRB must approve all advertising used to recruit subjects for the study. The protocol must be re-approved by the IRB, as local regulations require.

Progress reports and notifications of serious and unexpected adverse events will be provided to the IRB according to local regulations and guidelines.

15.2 Ethical Conduct of the Study

The study will be performed in accordance with ethical principles originating from the Declaration of Helsinki. Conduct of the study will be in compliance with ICH Good Clinical Practice, and with all applicable federal (including 21 CFR parts 56 & 50), state, or local laws.

15.3 Informed Consent Process

The site investigator will ensure the subject is given full and adequate oral and written information about the nature, purpose, possible risks and benefits of the study. Subjects must also be notified they are free to discontinue from the study at any time. The subject should be given the opportunity to ask questions and allowed time to consider the information provided.

The subject's signed and dated informed consent must be obtained before conducting any procedure specifically for the study. The site investigator must store the original, signed informed consent form. A copy of the signed informed consent form must be given to the subject.

17. APPENDIX A

GI Adverse Event Management Algorithm

[figure not shown]
Rule out non-inflammatory causes. If non-inflammatory cause is identified, treat accordingly and continue I-O therapy. Opiates/narcotics may mask symptoms of perforation. Infliximab should not be used in cases of perforation or sepsis.

Patients on IV steroids may be switched to an equivalent dose of oral corticosteroids (e.g. prednisone) at start of tapering or earlier, once sustained clinical improvement is observed. Lower bioavailability of oral corticosteroids should be taken into account when switching to the equivalent dose of oral corticosteroids.

Renal Adverse Event Management Algorithm

[figure not shown]
Rule out non-inflammatory causes. If non-inflammatory cause, treat accordingly and continue I-O therapy

Patients on IV steroids may be switched to an equivalent dose of oral corticosteroids (e.g. prednisone) at start of tapering or earlier, once sustained clinical improvement is observed. Lower bioavailability of oral corticosteroids should be taken into account when switching to the equivalent dose of oral corticosteroids.

Pulmonary Adverse Event Management Algorithm

[figure not shown]
Rule out non-inflammatory causes. If non-inflammatory cause, treat accordingly and continue I-O therapy. Evaluate with imaging and pulmonary consultation.

Patients on IV steroids may be switched to an equivalent dose of oral corticosteroids (e.g. prednisone) at start of tapering or earlier, once sustained clinical improvement is observed. Lower bioavailability of oral corticosteroids should be taken into account when switching to the equivalent dose of oral corticosteroids.

Hepatic Adverse Event Management Algorithm

Rule out non-inflammatory causes. If non-inflammatory cause, treat accordingly and continue I-O therapy. Consider Imaging for obstruction.

[figure not shown]
Patients on IV steroids may be switched to an equivalent dose of oral corticosteroids (e.g. prednisone) at start of tapering or earlier, once sustained clinical improvement is observed. Lower bioavailability of oral corticosteroids should be taken into account when switching to the equivalent dose of oral corticosteroids.

*I-O therapy may be delayed rather than discontinued if AST/ALT \leq 8 x ULN and T.bili \leq 5 x ULN.

**The recommended starting dose for grade 4 hepatitis is 2 mg/kg/day methylprednisolone IV.

Endocrinopathy Management Algorithm

[figure not shown]
Rule out non-inflammatory causes. If non-inflammatory cause, treat accordingly and continue I-O therapy. Consider visual field testing, endocrinology consultation, and imaging.

Patients on IV steroids may be switched to an equivalent dose of oral corticosteroids (e.g. prednisone) at start of tapering or earlier, once sustained clinical improvement is observed. Lower bioavailability of oral corticosteroids should be taken into account when switching to the equivalent dose of oral corticosteroids.

Skin Adverse Event Management Algorithm

Rule out non-inflammatory causes. If non-inflammatory cause, treat accordingly and continue I-O therapy.

[figure not shown]

Patients on IV steroids may be switched to an equivalent dose of oral corticosteroids (e.g. prednisone) at start of tapering or earlier, once sustained clinical improvement is observed. Lower bioavailability of oral corticosteroids should be taken into account when switching to the equivalent dose of oral corticosteroids.

*Refer to NCI CTCAE v4 for term-specific grading criteria.

[figure not shown]
Neurological Adverse Event Management Algorithm

Rule out non-inflammatory causes. If non-inflammatory cause, treat accordingly and continue I-O therapy.

Patients on IV steroids may be switched to an equivalent dose of oral corticosteroids (e.g. prednisone) at start of tapering or earlier, once sustained clinical improvement is observed. Lower bioavailability of oral corticosteroids should be taken into account when switching to the equivalent dose of oral corticosteroids.

Myocarditis Adverse Event Management Algorithm

Patients on IV steroids may be switched to an equivalent dose of oral corticosteroids (eg, prednisone) at start of tapering or earlier, once sustained clinical improvement is observed. Lower bioavailability of oral corticosteroids should be taken into account when switching to the equivalent dose of oral corticosteroids.

Prophylactic antibiotics should be considered in the setting of ongoing immunosuppression.

ATG = anti-thymocyte globulin; BNP = B-type natriuretic peptide; ECG = electrocardiogram; IV = intravenous; MRI = magnetic resonance imaging

320

Approved v19.0 930038243 20.0

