3.3 Inclusion/Exclusion Criteria- Part B

1. Must meet eligibility criteria for initiation of Part A with the exception of being allowed to have prior nivolumab in Part A of this protocol.
2. Must have evidence of either RECIST 1.1 defined Disease Progression or Stable Disease 1 year after initiating nivolumab therapy
3. Tumor biopsy prior to combination treatment is mandatory. If a biopsy/resection of a new lesion or primary tumor and slow freezing of fresh tissue for single cell RNAseq study (as specified in the CLM) is not feasible, the subject is not eligible for the study. All biopsies must be core needle or excisional. Fine needle aspirate is not acceptable.
4. Must not have had a Grade ≥ 3 irAE on nivolumab monotherapy (excluding endocrine toxicity managed with replacement therapy).
5. Must not have untreated brain metastases.
6. Must not have had major surgery or radiation therapy within 14 days of starting study treatment.
7. Must not have active autoimmune disease (see protocol for exceptions).
8. Must not have a concurrent medical condition requiring use of systemic corticosteroids with prednisone >10 mg per day.
9. Must not have had prior systemic therapy for Stage IV RCC (except for nivolumab as part of part A of this protocol).

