6.1.1 Dose Delay Criteria

Dose delay criteria apply for all drug-related adverse events (regardless of whether or not the event is attributed to nivolumab, ipilimumab or both). Study drugs (both agents if on induction phase of Part B) must be held/omitted until treatment can resume. Please see Appendix A for AE management guidelines.

Nivolumab and ipilimumab administration should be omitted for the following:

- Any Grade ≥ 2 non-skin, drug-related adverse event, with the following exceptions:
 - Grade 2 drug-related fatigue or laboratory abnormalities that do not require a treatment delay (with the exception of Grade 3 AST, ALT or total bilirubin in patients with normal baseline values-see below).
- Any Grade 3 skin, drug-related adverse event
- Any Grade 3 drug-related laboratory abnormality, with the following exceptions:
 - Grade 3 amylase or lipase abnormalities that are not associated with symptoms or clinical manifestations of pancreatitis do not require a dose delay. It is recommended to consult with the principal investigator for Grade 3 amylase or lipase abnormalities.
 - If a subject has a baseline AST, ALT, or total bilirubin that is within normal limits, delay dosing for drug-related Grade ≥ 2 toxicity
 - If a subject has baseline AST, ALT, or total bilirubin within the Grade 1 toxicity range, delay dosing for drug-related Grade ≥ 3 toxicity
- Any adverse event, laboratory abnormality, or intercurrent illness which, in the judgment of the site investigator, warrants delaying the dose of study medication.

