6.1.3 Discontinuation Criteria

Treatment should be permanently discontinued for the following:

- Any Grade 2 drug-related uveitis or eye pain or blurred vision that does not respond to topical therapy and does not improve to Grade 1 severity within the re-treatment period OR requires systemic treatment
- Any Grade 3 non-skin, drug-related adverse event lasting > 7 days, with the following exceptions for drug-related laboratory abnormalities, uveitis, pneumonitis, bronchospasm, diarrhea, colitis, neurologic adverse event, hypersensitivity reactions, and infusion reactions
 - Grade 3 drug-related uveitis, pneumonitis, bronchospasm, diarrhea, colitis, neurologic adverse event, hypersensitivity reaction, or infusion reaction of any duration requires discontinuation (**NOTE:** Subjects with Grade 3 diarrhea or colitis while on Part B ipilimumab/nivolumab combination therapy could resume nivolumab alone if toxicity resolves to at least Grade 1 off of immunosuppressive drugs by end of week 16. Nivolumab monotherapy cannot start until toxicity is resolved to at least Grade 1 off immunosuppression x 2 weeks and cannot begin before week 13 or after week 19.
- Grade 3 drug-related laboratory abnormalities do not require permanent treatment discontinuation except those noted below
 - Grade 3 drug-related thrombocytopenia > 7 days or associated with bleeding
 - Any drug-related liver function test (LFT) abnormality that meets the following criteria require discontinuation:
 - AST or ALT > 8 x ULN
 - Total bilirubin > 5 x ULN
 - Concurrent AST or ALT > 3 x ULN and total bilirubin > 2 x ULN

- Any Grade 4 drug-related adverse event or laboratory abnormality, except for the following events which do not require discontinuation:
 - Isolated Grade 4 amylase or lipase abnormalities that are not associated with symptoms or clinical manifestations of pancreatitis and:
 - Decrease to < Grade 4 within 2 weeks of onset in the absence of immunosuppressive therapy.
 - Decrease to < Grade 4 and maintain < Grade 4 for a minimum of 1 week after stopping immunosuppressive therapy.
 - Isolated Grade 4 electrolyte imbalances/abnormalities that are not associated with clinical sequelae and are corrected with supplementation/appropriate management within 72 hours of their onset
- Any dosing interruption lasting > 6 weeks (from scheduled dose) with the following exceptions:

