 - Dosing interruptions to allow for prolonged steroid tapers to manage drug-related adverse events are allowed. Prior to re-initiating treatment in a subject with a dosing interruption lasting > 6 weeks, the sponsor-investigator must be consulted. Tumor assessments should continue as per protocol even if dosing is interrupted
 - Dosing interruptions > 6 weeks that occur for non-drug-related reasons may be allowed if approved by the sponsor-investigator. **Prior to re-initiating treatment in a subject with a dosing interruption lasting > 6 weeks, the Principal Investigator must be consulted.** Tumor assessments should continue as per protocol even if dosing is interrupted.
- Any adverse event, laboratory abnormality, or intercurrent illness which, in the judgment of the site investigator, presents a substantial clinical risk to the subject with continued nivolumab or ipilimumab dosing

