6.3 Protocol Therapy Discontinuation

In addition to discontinuation from therapy related to toxicities as outlined above, a subject will also be discontinued from protocol therapy and followed per protocol under the following circumstances outlined below. The reason for discontinuation of protocol therapy will be documented on the electronic case report form (eCRF)

- Documented disease progression **NOTE:** Repeat scan should be performed in 4-6 weeks to confirm PD. A subject may be granted an exception to continue on treatment with confirmed radiographic progression if clinically stable or clinically improved. If PD confirmed patient can move to Part B and or go off study treatment.

- Completed 96 weeks of treatment with nivolumab (Part A) or 60 weeks of (nivolumab + ipilimumab for 12 weeks followed by nivolumab monotherapy for up to 48 weeks) (Part B). **NOTE:** 96 or 60 weeks of study medication are calculated from the date of first dose of each Part.
- Site investigator determines a change of therapy would be in the best interest of the subject
- Subject or legal representative (such as a parent or legal guardian) withdraws consent and requests to discontinue protocol therapy, whether due to unacceptable toxicity or for other reasons
 - In a subject decides to prematurely discontinue protocol therapy (“refuses treatment”), the subject should be asked if he or she may still be contacted for further scheduled study assessments. The outcome of that discussion should be documented in both the medical records and in the eCRF.
- Female subject becomes pregnant
- Unacceptable adverse experiences
- Intercurrent illness that prevents further administration of treatment
- Protocol therapy is interrupted for > 6 weeks (calculated from the date of the first missed dose). Any potential exceptions to this criterion must be discussed with and approved by the study chair.
- Noncompliance with protocol treatment or procedure requirements
- The subject is lost to follow-up
- Administrative reasons

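### The hepatic footnote in Appendix A omits the combined AST/ALT-and-bilirubin stopping rule of Section 6.1.3, so its words allow a hold where 6.1.3 requires a permanent stop (minor, safety text)

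*Combined protocol and SAP*

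**What the plan says.** Two parts of the protocol set liver thresholds for stopping study drug.

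**Section 6.1.3, Discontinuation Criteria.** This is a list of reasons for permanent discontinuation. For the liver it reads "Any drug-related liver function test (LFT) abnormality that meets the following criteria require discontinuation", and then gives three criteria:

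1. AST or ALT above 8 x ULN
2. total bilirubin above 5 x ULN
3. "Concurrent AST or ALT > 3 x ULN and total bilirubin > 2 x ULN"

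**Appendix A, Hepatic Adverse Event Management Algorithm, asterisked footnote.** "I-O therapy may be delayed rather than discontinued if AST/ALT" is no more than 8 x ULN and total bilirubin is no more than 5 x ULN. The footnote states no limit for the two being raised together.

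Three other places bear on how the two texts relate:

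- Section 6.1.1 sends sites to the appendix: "Please see Appendix A for AE management guidelines".
- Section 6.3 treats toxicity stopping as already settled in the preceding sections: "In addition to discontinuation from therapy related to toxicities as outlined above".
- Section 6.1.2, on resuming treatment, says that combined Grade 2 AST/ALT and bilirubin values that meet the discontinuation parameters should lead to a permanent stop. For those parameters it cites Section 6.3.3, which does not exist; they are in 6.1.3.

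No sentence says which text prevails if Section 6 and Appendix A differ.

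**The concern.** The two limits in the footnote are the exact complements of the first two criteria in 6.1.3. A reader could therefore take it as a full restatement of when a hold is acceptable, when one of the three mandatory stops is missing.

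The practical risk is narrow. A site managing a liver event from the appendix page holds the drug, sees the values recover, and restarts nivolumab in Part A or study drug in Part B, although 6.1.3 required a permanent stop. What is at stake is the safety of the individual patient and consistent handling across sites. No endpoint definition, power calculation or error rate depends on it.

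**Working it through.** The plan gives no figure to reproduce here, so the check compares the two rules as sets.

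**Inputs.** Let A be the higher of AST and ALT, and B total bilirubin, both in multiples of ULN, for a drug-related event. I read the footnote's AST/ALT limit as applying to both enzymes.

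- Stop required (Section 6.1.3): A > 8, or B > 5, or (A > 3 and B > 2).
- Delay permitted (Appendix A footnote): A ≤ 8 and B ≤ 5.

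**Overlap.** Within A ≤ 8 and B ≤ 5 the first two stop criteria cannot be met. Only the third can, so the texts conflict when

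3 < A ≤ 8 and 2 < B ≤ 5.

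**Spot checks**

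| A | B | Section 6.1.3 | Footnote | Conflict |
|---|---|---|---|---|
| 6 | 4 | stop (6 > 3 and 4 > 2) | delay permitted (6 ≤ 8, 4 ≤ 5) | yes |
| 8 | 5 | stop (8 > 3 and 5 > 2) | delay permitted | yes, upper corner |
| 3.1 | 2.1 | stop (3.1 > 3 and 2.1 > 2) | delay permitted | yes, just inside lower corner |
| 3 | 2 | no liver stop | delay permitted | no |
| 6 | 1.9 | no liver stop (1.9 is not > 2) | delay permitted | no |
| 8.1 | 4 | stop (8.1 > 8) | delay not permitted | no |

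**After the fix.** If the footnote also requires that A > 3 and B > 2 do not hold together, the permitted set becomes A ≤ 8, B ≤ 5 and not (A > 3 and B > 2). That is the complement of the stop set, so the overlap is empty.

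**Does another provision catch the restart?**

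- Section 6.1.2 is the most direct safeguard, because it governs resumption and addresses combined elevations. Its cover is partial: it names Grade 2 values, and its cross-reference leads nowhere.
- Section 3.3, item 4, bars Part B entry after a Grade 3 or higher immune-related event on nivolumab, apart from endocrine toxicity managed with replacement. It does not govern a restart within Part A or within Part B.
- Section 6.1.3 on long holds: "Prior to re-initiating treatment in a subject with a dosing interruption lasting > 6 weeks, the sponsor-investigator must be consulted". A hold of 6 weeks or less carries no such requirement.
- Section 6.1.3 also requires a stop for any event that, in the site investigator's judgment, "presents a substantial clinical risk to the subject with continued nivolumab or ipilimumab dosing". This depends on judgment and sets no threshold.

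Together these lower the risk. They do not fully cover a hold of 6 weeks or less followed by recovery and restart.

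**The case against.** The strongest objection is that the body text already settles the matter. Section 6.1.3 is worded as a requirement and the footnote as a permission, in an appendix that 6.1.1 calls guidelines. A site that stops the patient complies with both, and a site that follows Section 6 does not go wrong. That stands, and it is why the point is minor. It does not remove the need for a correction, because no precedence sentence exists and 6.1.1 directs sites to the appendix for managing adverse events.

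Second, the footnote hangs by an asterisk from a figure that cannot be seen. The box that carries the asterisk may cover only some events, or may treat combined elevation separately. That also stands: the range above is an upper bound. It does not alter the footnote's own stated condition, which is a complete sentence.

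Third, the footnote does not try to restate all of 6.1.3. It also omits the stop for a Grade 3 non-skin event lasting more than 7 days, the stop for interruptions over 6 weeks, and the investigator-judgment stop. So the two texts can be said to agree outside the conflict range only on the three liver-test thresholds.

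A reader might infer that the protocol as a whole allows re-treatment after combined liver injury, or that the appendix overrides Section 6. The documents support neither: 6.1.3 forbids it and 6.1.2 repeats the stop for combined Grade 2 values. Nor do they support reading the missing clause as a fault of the whole algorithm, since the figure is not available.

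**Conclusion.** The footnote is wrong as written, at minor severity and with moderate confidence. Its words permit a hold for drug-related events that fall in the overlap range derived above, where Section 6.1.3 requires permanent discontinuation. This rests on the visible footnote text, on Section 6.1.3 being the controlling rule, and on no contrary wording in the unseen figure. No toxicity-grade cut-offs were used. How many patients would fall in the range cannot be derived from the documents, and no claim is made about how often a wrong restart would occur.

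**What to change.** Preferred: after the two existing limits in the Appendix A hepatic footnote, add *and not concurrent AST/ALT > 3 x ULN with T.bili > 2 x ULN; Section 6.1.3 governs*.

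Alternative: the appendix ends with its own approval and version line, so it may be a controlled page that is awkward to edit. In that case add one sentence to Section 6.1.1: *where Appendix A and Section 6.1.3 differ, Section 6.1.3 governs*.

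With either, change the reference in Section 6.1.2 from 6.3.3 to 6.1.3, so that the resume rule points to the liver criteria.

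Cost: one clause or one sentence, plus one cross-reference, in a short amendment. No visits, tests or patients are added.
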